Deep brain stimulation (DBS) has become an evidence-based treatment for movement disorders such as Parkinson's disease. Recent animal studies of DBS suggest that neuronal subpopulations may be specifically activated by burst-type DBS and that this type of electrical stimulation programming may improve the efficacy and durability of DBS. Burst-type DBS is defined as a novel stimulation protocol in which intermittent bursts of traditional high-frequency rectangular wave stimulation are delivered. Implanted pulse generators (IPGs) have the capability to deliver such stimulation by setting specific "on" and "off" times, however there is no published human data on the results of such programming in patients undergoing DBS for movement disorders such as PD.

Primary Objective

The primary objective is to determine change in the UPDRS-III motor score in the medication OFF state with burst-type DBS programming in the acute setting (after 30 minutes) and then after 6 months and 12 months for patients with bilateral subthalamic nucleus DBS for Parkinson's disease.

Study Design:

Randomized, double-blind cross-over study with N= 5 patients implanted with bilateral subthalamic nucleus DBS.

Study Site:

Allegheny General Hospital
Neuroscience Institute
[name]
[name]

Study Population

Patients for this study (N= 5) should have bilateral STN-DBS (with Boston scientific Gevia or Genus technology) implanted for Parkinson's disease. The patients should be on stable DBS programming settings and stable medication regimens defined as no DBS programming changes or Parkinson's disease medication changes over past 2 weeks. The DBS implantation should have been performed by either [name], MD or [name], MD at Allegheny General Hospital and implantation surgery must have occurred a minimum of 6 months prior to the day of enrollment.

Recruitment Strategy

Subjects will be recruited from the DBS practice of investigator neurosurgeons [name] MD and [name] MD. Patients will be identified by the neurosurgeons as well as by DBS nurse [name] RN and physician assistant [name] PA-C.

Recruitment will stop when approximately 5 subjects are enrolled. It is expected that approximately 15 subjects will be enrolled to produce 5 evaluable subjects.

Subject Replacement

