In the event that consented subjects are unable to complete study procedures for any reason (e.g. unable to attend visits, adverse reaction to burst programming, or other concerns determined by primary investigator), subjects will be withdrawn from the study and primary investigator may screen and enroll replacement subjects(s) to ensure the number of completed subjects equals 5.

Inclusion Criteria

1. Adult patients (male and female) ages 18-85
2. Bilateral DBS-STN (subthalamic nucleus) target for idiopathic Parkinson's disease implanted minimum 6 months prior to the day of study enrollment
3. Stable DBS programming settings and Parkinson's disease medications defined as no changes to either within past 2 weeks
4. Comfortable using DBS controller to turn off device prior to study visits
5. Able to provide informed consent and complete follow-up visits

Exclusion Criteria

1. DBS technology other than Boston scientific Genus/Gevia
2. Unable to complete follow-up visits
3. DBS brain targets other than STN (subthalamic nucleus)
4. Signs of progressive cognitive decline

Subject Completion/Withdrawal

Subjects may withdraw from the study at any time without prejudice to their care. They may also be discontinued from the study at the discretion of the Investigator for lack of adherence to study treatment or visit schedules, AEs, or due to medical illness which complicates follow-up. The Investigator or the Sponsor (if applicable) may also withdraw subjects who violate the study plan, or to protect the subject for reasons of safety or for administrative reasons. It will be documented whether or not each subject completes the clinical study. If the Investigator becomes aware of any serious, related adverse events after the subject completes or withdraws from the study, they will be recorded in the source documents and on the CRF.

The study duration per subject will be up to 365 days.

Description of Devices and Assessments

DBS System

Boston Scientific Neuromodulation (BSN) Vercise™ System: A neurostimulation device consisting of an implantable pulse generator (IPG), integrated rechargeable battery, two DBS leads, two DBS extensions, Burr Hole Cover, surgical tools, GUIDE XT Software and external devices (programming system, remote control, and charging system). The implanted pulse generator (IPG) for this study will be either the Gevia or Genus model.

UPDRS (United Parkinson's Disease Rating Scale)

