- Unblinded examiner will then turn the DBS ON to the patient's baseline DBS settings continuously ON or to burst DBS mode (baseline DBS settings for the patient with DBS set to 1 sec ON, 4 sec OFF), based on results of randomization. The patient will be blinded to this programming change and will be kept at this initial setting for 30 minutes.
- Next, a blinded examiner who did not perform the programming change will perform a UPDRS-III evaluation. Next, the DBS will be turned off for 15 minutes to permit for a washout period.
- Next, the DBS will be turned on by the unblinded examiner to the alternate setting (burst DBS in case that the patient first was turned on with their baseline DBS setting or baseline DBS setting in case that the patient was first turned on with burst DBS setting) and kept on this setting for 30 minutes.
- After 30 minutes, the blinded examiner will perform another UPDRS-III evaluation. Patients, who are blinded to the stimulation setting, will be asked if they preferred one stimulation mode over the other.
- If any adverse events occur with burst DBS mode, the unblinded examiner will decrease the amplitude of the DBS by 0.5mA increments until the adverse events abate. If there are not persistent adverse events with 30 minutes of burst DBS mode, the patient will be kept in burst DBS mode at the end of first visit and will be allowed to take their Parkinson's disease medications.

Figure 1. Visit 1 Assessment Schema

Randomization Procedure

Subjects will be randomized to determine which DBS setting is initially programmed during visit one. All subjects will be programmed to both settings over the course of the visit, but the order is randomized to ensure appropriate blinding of the UPDRS assessor. Subjects have a 50% chance of being randomized to the “burst” mode, and a 50% chance of being randomized to the “baseline” mode. Following the initial UPDRS assessment (Meds OFF/DBS OFF), the study coordinator or unblinded assessor will use a computerized randomization system to determine which DBS setting the subject receives first.

Visit Two (6 months +/- 30 Days)

- Parkinson’s disease dopaminergic medications will be withdrawn overnight to establish medication-OFF state and DBS will be turned OFF overnight for establishing DBS-OFF state.

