- Examiner will establish a UPDRS-III baseline with medication-OFF, DBS-OFF state. Examiner will then turn the DBS ON to the burst DBS state and keep ON for 30 minutes. After 30 minutes the examiner will perform another UPDRS-III evaluation and will ask about any adverse effects. Patients will then be allowed to take their Parkinson’s disease medications and will be kept on the burst mode DBS state.
- Patients will be asked if they prefer the burst mode DBS state to their baseline settings before the study.

Visit Three (12 months +/- 30 days)

- Parkinson’s disease dopaminergic medications will be withdrawn overnight to establish medication-OFF state and DBS will be turned OFF overnight for establishing DBS-OFF state.
- Examiner will establish a UPDRS-III baseline with medication-OFF, DBS-OFF state. Examiner will then turn the DBS ON to the burst DBS state and keep ON for 30 minutes. After 30 minutes the examiner will perform another UPDRS-III evaluation and will ask about any adverse effects. Patients will then be allowed to take their Parkinson’s disease medications and will be kept on the burst mode DBS state.
- Patients will be asked if they prefer the burst mode DBS state to their baseline settings before the study. At the conclusion of the study, patients will be asked if they want to continue to use burst DBS state or if would prefer to be programmed back to their pre-study baseline DBS settings.

Phone Follow-Up Visits

Phone follow up calls will be completed by study personnel to determine subject’s programming preference at 1 week, 1, 3 and 9 months post programming changes.

Table 1. Schedule of Study Events

Activities	Screening/ Enrollment	Visit 1 (Baseline)	Visit 2 Month 6 +/- 30 days	Visit 3 Month 12 +/- 30 days	Phone Follow-up ⁴
Informed Consent	x				
Demographics	x				
Medical History	x				
Parkinson's Medications	x	x	x	x	x
Concomitant medications	x	x	x	x	x
Adverse Events		x	x	x	x
Serious Adverse Events		x	x	x	x
Adverse Device Effects		x	x	x	
UPDRS III (Meds OFF ¹ /DBS OFF ²)		x	x	x	
UPDRS III (Meds OFF ¹ /DBS ON- Burst)		x	x	x	
UPDRS III (Meds OFF ¹ /DBS ON- Baseline ³)		x			

¹ Parkinson's disease dopaminergic medications should be withdrawn overnight to establish medication-OFF state

² DBS should be turned off overnight to establish DBS-OFF state

³ DBS should be programmed to the baseline settings patient had before study entry

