Adverse event information will be collected throughout the study, beginning once the patient is enrolled in the study and monitored until each event is adequately resolved or explained. An AE or SAE description (including the nature of the event, date and time of onset, determination of non-serious versus serious, intensity, duration, causality, and outcome of the event) will be recorded on the case report forms by the investigator or research coordinator. A summary report of all serious adverse events will be provided to the reviewing IRB annually. Serious adverse events will be reported within 5 days of the investigator learning of the event to the reviewing IRB.

Secondary Endpoints

Burst DBS may require less energy and therefore a secondary endpoint we will include is a calculation of IPG (implanted pulse generator) or battery longevity. Secondary endpoints will also patient preference for stimulation mode.

Statistical Methods

Statistics will be performed using Mann-Whitney-U test and p-value < 0.05 will be required for statistical significance.

Regulatory and Ethical Considerations

Compliance Statement

This study will be conducted in full accordance all applicable Allegheny Health Network Research Policies and Procedures and all applicable Federal and state laws and regulations including 45 CFR 46, 21 CFR Parts 50, 54, 56, 312, 314 and 812 and the Good Clinical Practice: Consolidated Guideline approved by the International Conference on Harmonisation (ICH). All episodes of noncompliance will be documented.

The investigators will perform the study in accordance with this protocol, will obtain consent and assent, and will report unanticipated problems involving risks to subjects or others in accordance with the AHN IRB Policies IRB Policies and Procedures and all federal requirements. Collection, recording, and reporting of data will be accurate and will ensure the privacy, health, and welfare of research subjects during and after the study.

Risk Assessment

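### The only planned test, Mann-Whitney U, is for independent groups, but every UPDRS-III score comes from the same cross-over patients

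*Combined protocol and SAP*

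**What the plan says.** Statistical Methods contains a single sentence: "Statistics will be performed using Mann-Whitney-U test and p-value < 0.05 will be required for statistical significance". No other analysis appears in the document.

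Study Design describes a "Randomized, double-blind cross-over study with N= 5 patients implanted with bilateral subthalamic nucleus DBS". Under Randomization Procedure, "All subjects will be programmed to both settings over the course of the visit", and only the order is randomised. Visit One and Table 1 also call for a score with DBS off. At Visits Two and Three the same patients are scored with DBS off and then on burst: "Examiner will then turn the DBS ON to the burst DBS state and keep ON for 30 minutes". Each completer therefore gives 7 UPDRS-III scores (3 + 2 + 2), and there is no parallel group.

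The Primary Objective is change in UPDRS-III, medication OFF, at 30 minutes, 6 months and 12 months. It does not name the score from which change is measured.

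On numbers, Recruitment Strategy states: "It is expected that approximately 15 subjects will be enrolled to produce 5 evaluable subjects". Subject Replacement allows new patients "to ensure the number of completed subjects equals 5".

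**The concern.** Mann-Whitney takes its reference distribution from two unrelated samples. Here the two samples are the same people, and patients with Parkinson's disease can differ widely in severity. A cross-over removes that between-patient spread by comparing each patient with himself or herself. The named test puts the spread back into the noise.

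With 5 completers, the within-patient comparison is the main source of precision. A non-significant result could therefore reflect the test rather than burst stimulation, and no effect estimate or confidence interval is planned that would help a reader tell the two apart. The protocol says there are no published human data on this programming and plans publication, so a misleading null result would matter.

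The sentence also does not say which scores are compared, whether the test is one- or two-sided, or which patients are included. Those choices could be made after the data are seen.

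**Working it through.** **Inputs from the documents.** Mann-Whitney U at 0.05 (Statistical Methods); 5 completers (Study Design, Subject Replacement); both settings in every patient, with 50:50 order (Randomization Procedure). N = 5 comes with no effect size, SD, correlation or power, so there is no sample size calculation to reproduce.

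**Assumptions.** Two-sided exact test, normal scores, SD 10, within-patient correlation r from 0 to 0.9. Power depends only on the ratio of difference to SD, so 8 points means 0.8 SD and 20 points means 2 SD.

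**1. What the pairing is worth.** The standard error of a mean within-patient difference is SD × √(2(1 − r)/n).
- r = 0: 10 × √(2/5) = 6.3 points
- r = 0.5: 10 × √(1/5) = 4.5 points
- r = 0.8: 10 × √(0.4/5) = 2.8 points

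Mann-Whitney judges the data as though r were 0.

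**2. Exact rejection rule, 5 v 5.** There are C(10,5) = 252 arrangements. U ≤ 2 gives two-sided p = 0.0317 and U ≤ 3 gives 0.0556. The test therefore rejects at U ≤ 2, with level 0.032 if the scores were independent.

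**3. Simulation with 5 patients** (at least 100,000 data sets per scenario; MW = Mann-Whitney, t = paired t):

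| r | MW type I error | 8 points: MW v t | 20 points: MW v t |
|---|---|---|---|
| 0 | 0.032 | 14% v 17% | 68% v 66% |
| 0.5 | 0.008 | 10% v 28% | 71% v 91% |
| 0.7 | 0.003 | 9% v 42% | 72% v 99% |
| 0.8 | 0.0014 | 8% v 57% | 72% v 99.9% |
| 0.9 | 0.0002–0.0004 | 7–8% v 84% | 72% v over 99.9% |

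More pairs do not remove the gap. For 8 points at r = 0.7 (60,000 data sets per scenario), power is 31% v 83% with 10 pairs and 56% v 96% with 15.

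**4. An invented example.** Scores of 50, 42, 35, 28, 20 fall to 44, 37, 31, 23, 16. Every patient improves, by 6, 5, 4, 5 and 4 points. Mann-Whitney gives p = 0.69; the paired t gives p = 0.0002; the two-sided signed-rank test gives 0.0625, the lowest value it can take.

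**5. The valid cross-over use of Mann-Whitney.** This compares within-patient period differences between the two order groups. The smallest two-sided p is 2/C(5,2) = 0.20 for a 3 v 2 split and 2/C(5,1) = 0.40 for 4 v 1. It cannot reach 0.05, and it does not apply at months 6 and 12, where no setting or order is randomised.

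**6. The obvious nonparametric replacement.** The signed-rank minimum two-sided p is 2/2⁵ = 0.0625 with 5 pairs and 2/2⁶ = 0.031 with 6. One-sided with 5 pairs it is 1/2⁵ = 0.031.

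**The case against.** **The document says more than the one sentence.** The Primary Objective gives the outcome, condition and time points, and each visit starts with a DBS-off score, so burst against same-day DBS-off is a natural reading of change. The wording on 5 evaluable and 5 completed patients points to a completers analysis. Both are fair readings, but neither is stated as the analysis. Whether Visit 1 burst against baseline setting is also primary remains open. With about 15 enrolments expected and non-completers replaced, more than 5 patients may have a Visit 1 pair. Taken alone, these gaps would be missing detail rather than error.

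**The size of the loss is assumed.** This stands: it runs from none (r = 0, 20 points) to very large (r = 0.9, 8 points). It also depends on using the exact test. A large-sample version without continuity correction would reject at U ≤ 3 (z = −9.5/4.79 = −1.98, p = 0.047), and power for 8 points at r = 0.8 would be about 14% rather than 8%. The direction does not change.

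**The error is conservative, and N = 5 limits any test.** Both are true. Under positive correlation the named test does not inflate false claims of benefit, and at r = 0.5 even the paired t has only 28% power for 8 points. That does not justify discarding the pairing, or making p < 0.05 the only stated criterion.

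**The replacement is imperfect.** This also stands. Five differences cannot verify normality. With strongly skewed differences the paired t has a true type I error of about 12% (exponential) to 18% (lognormal, sigma 1). This is a reason to rest on estimates and individual values, not to keep an independent-groups test.

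**Conclusion.** The concern holds and must be fixed. The only stated method does not match the design of the primary outcome. That conclusion needs no assumption: it follows from setting Statistical Methods beside Study Design, Randomization Procedure and the visit descriptions. The one independent-groups analysis that would be valid is not described and cannot go below p = 0.20 with 5 patients.

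The consequence is an over-conservative test and usually lost power, not false positives. Its size is illustrative. With normal scores, SD 10, an exact test and 8 points, power is 10% against 28% at r = 0.5 and 8% against 57% at r = 0.8. The loss is small or absent near r = 0, and proportionally smaller for very large effects.

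**What to change.** Replace the sentence in Statistical Methods with a within-patient analysis of UPDRS-III differences:

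- **Contrasts:** burst minus baseline setting at Visit 1; burst minus same-day DBS-off at Visit 1, month 6 and month 12. Before analysis, the sponsor names the primary contrast and time point from its own objective, and the sidedness.
- **Method:** a paired t analysis, or a mixed model with a patient random effect. Report the mean difference with its 95% confidence interval and list every individual difference.
- **Sensitivity:** a period-adjusted analysis of the Visit 1 burst v baseline contrast.
- **Analysis set:** state whether it is the 5 completers or all patients with a Visit 1 pair.
- **p-values:** present them as exploratory beside the estimates. If a signed-rank test is preferred, first check that it can reach the chosen level with the available pairs.

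The cost is a few sentences, with no new data or patients. The price is reliance on approximate normality, which is why individual values and the exploratory label are needed. Period adjustment also costs some power (48% against 57% for 8 points at r = 0.8 with a 3:2 order split). It is impossible if all 5 patients get the same order, which has probability 2/2⁵ = 6.25% under simple 50:50 randomisation.

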Risks of the study are minimal. Patients may experience a temporary worsening of motor symptoms when they stop medications the night before patient visits and may also experience a temporary worsening of motor symptoms when programmed into burst-type DBS. These motor symptom changes, if they do occur, would be reversible, and no patient will be required to continue using burst-type DBS after the first visit if they do not want to or if they find the motor symptom changes worse or bothersome. Patients may contact a member of the study team if they wish to exit the study or stop using burst-type DBS programming at any time.

Potential Benefits of Participation

The potential benefits of burst-type DBS include the potential of better motor symptom control including improved tremor, improved rigidity, and improved dyskinesias. An additional benefit may be that burst-type DBS may require lower energy for treatment and could therefore prolong DBS implanted pulse generator (IPG) life.

Confidentiality

All data and records generated during this study will be kept confidential in accordance with Institutional policies and HIPAA on subject privacy and that the Investigator and other site personnel will not use such data and records for any purpose other than conducting the study. All patient data will be de-identified and kept on a secure computer within the Neuroscience Research Department at Allegheny General Hospital.

No identifiable data will be used for future study without first obtaining IRB approval. The investigator will obtain a data use agreement between the provider (the PI) of the data and

any recipient researchers (including others at AHN) before sharing a limited dataset (PHI limited to dates and zip codes).

Data Safety Monitoring

The research team, including the PI, will meet a minimum of every 12 months to review accruals, adverse events, potential breaches in confidentiality and any unanticipated problems related to this research. Any identified reportable events or breaches in confidentiality will be reported immediately to AHNRI IRB and AHN Privacy Department. Any events or changes in the risk/benefit ratio affecting decisions about study continuation will be submitted to the IRB immediately via a prompt report form.

Payment to Subjects

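### The objective is to determine the change in UPDRS-III, but the only planned inference is an unpaired p < 0.05 test, which gives no estimate or interval and, with 5 patients, will usually miss a 5- to 10-point difference

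*Combined protocol and SAP*

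**What the plan says.** The Primary Objective is worded as estimation: "The primary objective is to determine change in the UPDRS-III motor score in the medication OFF state with burst-type DBS programming", at three times (30 minutes, 6 months, 12 months). Study Design gives the size and structure: "Randomized, double-blind cross-over study with N= 5 patients implanted with bilateral subthalamic nucleus DBS". Subject Replacement allows the investigator to "enroll replacement subjects(s) to ensure the number of completed subjects equals 5", so the analysis set is five completers.

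The data are paired. Under Randomization Procedure, "All subjects will be programmed to both settings over the course of the visit", and only the order is random. Table 1 schedules UPDRS-III with DBS off and with burst at Visits 1, 2 and 3, and on the patient's usual settings at Visit 1 only.

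Statistical Methods is one sentence. It names the Mann-Whitney U test and adds that "p-value < 0.05 will be required for statistical significance". It names no contrast, estimate, interval or precision target, and does not say how a non-significant result will be interpreted. Secondary Endpoints adds a calculation of battery longevity and patient preference, with no method for either. Potential Benefits of Participation says that "burst-type DBS may require lower energy for treatment and could therefore prolong DBS implanted pulse generator (IPG) life".

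**The concern.** A p-value does not determine a change. If Statistical Methods is followed as written, the trial can report significant or not significant at each time, but not how many points UPDRS-III moved or how precisely that is known. The plan describes burst programming for movement disorders as having no published human data, so the size of the change and its uncertainty are what readers will need.

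Two features make this worse. The Mann-Whitney test treats the two sets of five scores as independent groups, so differences between patients enter as noise although the crossover removes them. And five patients are few enough that non-significance is the likely result for a moderate real difference in either direction. Reported alone, such a result leaves open anything from a useful gain to a material loss of motor control. Any energy saving would then appear in the report with no bound on its motor cost.

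**Working it through.** The plan states N = 5 without a power calculation, SD, target difference or precision goal, so it has no figure to reproduce.

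**Inputs.** From the documents: 5 completed patients, each scored under both settings at Visit 1; Mann-Whitney U; threshold 0.05 (sidedness is not stated, two-sided assumed); UPDRS-III from 0 to 108. Assumed: between-patient SD 6 to 12 points; SD of within-patient differences 5 to 10 points (6 to 10 for the Mann-Whitney simulation); true differences of 5 and 10 points; normal data.

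**1. Rejection region of the planned test.** Two groups of 5 have C(10,5) = 252 equally likely rank arrangements.
- U ≤ 2 covers 1 + 1 + 2 = 4 arrangements: two-sided p = 2 × 4/252 = 0.032.
- U ≤ 3 covers 7 arrangements: two-sided p = 2 × 7/252 = 0.056.

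Significance therefore requires U ≤ 2 in one direction or the other.

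**2. Detection rate of the planned test on paired data.** Score = patient effect (between-patient SD) + occasion error (SD of differences/√2), with the true difference added to one setting; 200,000 simulated trials per row.

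| Between-patient SD | SD of differences | 5-point difference | 10-point difference |
|---|---|---|---|
| 6 | 6 | 5.9% | 34.9% |
| 6 | 10 | 4.9% | 20.8% |
| 12 | 6 | 0.8% | 7.1% |
| 12 | 10 | 1.2% | 6.2% |

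The ranges are about 1 to 6% and 6 to 35%. If the SD is instead defined as the total SD of a single score (8 to 15) with difference SD 5 to 10, they are 0.4 to 8% and 4 to 30%.

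The test is not blind to large effects. For a true shift of 2 total SDs it rejects 68 to 72% of the time, at within-patient correlations of 0 to 0.8.

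**3. A paired t analysis of the same five patients.** Power = P(|T| > 2.776), where T is noncentral t with 4 df and noncentrality = difference × √5/SD.

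| SD of differences | 5 points | 10 points |
|---|---|---|
| 5 | 40% | 91% |
| 6 | 30% | 79% |
| 8 | 19% | 56% |
| 10 | 14% | 40% |

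Pairing recovers a good deal, but a 5-point difference is still missed at least 60% of the time.

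**4. Precision if an interval is reported.** Half-width = t(0.975, 4)/√5 × SD = 2.776/2.236 × SD = 1.24 × SD. For SD 5, 6, 8 and 10 this is 6.2, 7.4, 9.9 and 12.4 points.

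**5. Would a paired rank test be enough?** With five differences all in one direction, the signed-rank test gives its smallest two-sided p, 2/2⁵ = 0.0625. It can never reach 0.05.

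**The case against.** The strongest reply is that this is a five-patient exploratory study, and that nothing in it claims burst is as good as usual settings. That is correct. A reader might infer that a non-significant burst-versus-usual result would be presented as equal motor control at lower energy. The documents do not support that reading. They state no non-inferiority or equivalence aim and give no rule for a null result. The introduction and Potential Benefits express a hope of better motor control and put energy second, as a further possible benefit. Battery longevity is one secondary calculation and is not tied to any motor criterion. The misreading is a risk to guard against, not a plan to criticise. For the same reason, the lack of a stated acceptable loss is not an error.

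A second stronger reading also fails: that non-significance is expected even when burst is clearly worse, whichever test is used. A paired t analysis detects a 10-point difference 91% of the time at SD 5 and 79% at SD 6.

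Three further points stand. Every detection rate rests on assumed SDs, so only the ranges should be quoted. The objective does not name burst versus usual settings, which can be assessed only at Visit 1, so a remedy confined to that contrast would leave the 6- and 12-month changes unaddressed. And battery longevity and preference are planned outputs, so the accurate statement is that the test is the only planned inferential analysis.

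None of this answers the central point. Whether the hope is improvement or maintenance, an unpaired p-value does not determine a change.

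**Conclusion.** The concern holds as a mismatch between objective and analysis. The objective asks for the size of a change at three times; the only inferential method is a significance test that gives no size, ignores the pairing and has little power at N = 5. Under the assumed SDs it detects a 5-point difference about 1 to 6% of the time and a 10-point difference about 6 to 35%, against 14 to 40% and 40 to 91% for a paired t analysis over SDs of 5 to 10. Those rates depend on the assumed SDs and on normality. The absence of an estimate and interval, the neglect of pairing and the 1.24 × SD half-width do not depend on the assumed SDs. The finding is not that the trial plans to claim equivalence. This should be changed before the data are analysed, and preferably before the first patient is scored.

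**What to change.** In Statistical Methods, replace the Mann-Whitney p < 0.05 rule as the basis for conclusions:

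- List every patient's within-patient change, and report the mean change with a 95% CI (t, 4 df), for burst minus DBS-OFF at Visits 1, 2 and 3 and for burst minus usual settings at Visit 1.
- State that a non-significant result, or an interval that includes zero, will not be read as equal motor control.
- Present the battery-longevity result beside the Visit 1 burst-minus-usual interval.
- Only if the sponsor wishes to claim maintained motor control: state the acceptable loss in advance, and make the claim only if the interval excludes it. This is conditional, because the documents state no such aim.

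Moving to a signed-rank test at p < 0.05 is not a remedy, for the reason in step 5 of the working.

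The cost is a few sentences and no new data, since Table 1 already collects every score needed. The drawbacks are wide intervals, reliance on approximate normality that five patients cannot verify (hence the individual values), and a burst-versus-usual result that will probably have to be reported as inconclusive.
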